Appendix 3 PK Blood Sampling, EEG and ECG Schedule During Dosing Periods

Time Relative to Dose	Part A (SAD, HV)						Part B (MAD, HV)					
	Day 1			Day 2 ¹			Day 1-7					
							Cohorts 1-2			Cohort 3		
	PK ²	ECG ³	EEG ⁴	PK ²	ECG ³	EEG ⁴	PK ²	ECG ³	EEG ⁴	PK ⁵	ECG ³	EEG ⁴
Predose	X	X	X	X		X	X	X	X	X	X	X
15 minutes	X					X						
30 minutes	X					X		X	X			X
1 hour	X	X				X	X		X	X		
2 hours	X	X				X			X			
4 hours	X	X				X			X			
8 hours	X	X				X			X			
8.5 hours									X			
9 hours									X			
10 hours									X			
12 hours	X					X			X			
16 hours	X	X							X			
24 hours		X	X	X		X			X			X
30 hours				X								

Abbreviations: ECG = electrocardiogram; EEG = electroencephalography; HV = healthy volunteer; MAD = multiple ascending dose; PK = pharmacokinetics; SAD = single ascending dose.

¹ For Part A (SAD), Day 2 is the 24-hour timepoint after last study drug administration. For Part B (MAD), Day 8 is the 24-hour timepoint after last study drug administration (Cohorts 1 and 2) and 24-hours post morning dose (Cohort 3). This visit will be used to collect only the “24-hour” samples.

² During Part A (SAD), PK samples and time windows are predose, and 15 minutes (± 2 minutes), 30 minutes (± 2 minutes), 1 hour (± 5 minutes), 2-, 4-, 8-, 12-, and 24- and 30-hours (± 30 minutes) postdose. During Part B (MAD Cohorts 1 and 2), PK samples will be taken at predose and 15 minutes (± 2 minutes), 30 minutes (± 2 minutes), 1-hour (± 5 minutes), 2-, 4-, 8-, and 12- hours (± 15 minutes) postdose on Days 1, 4 and 7. The timing and number of PK samples may be altered depending on emerging data and safety profile.

³ Part A (SAD) ECGs and time windows are Screening, Day -1, predose, 1 hour (± 2 minutes), 2-, 4-, 8-, and 16-hours (± 5 minutes), and 24-hours (± 30 minutes). For the MAD part of the study, ECGs will be undertaken at Screening, Day -1, predose, and 1-hour postdose (± 30 minutes) on Day 1 to Day 7. ECGs will be measured with the subject to be seated or semi-supine after resting for at least 3 minutes.

⁴ A 1-hour (± 15 minutes) EEG will be collected during Part A (SAD) at screening under sleep deprived conditions (after only 4 hours of sleep) and 24 hour ambulatory EEGs will be collected from at least 30 minutes (± 10 minutes) predose until 24 hours (± 1 hour) postdose (Day 1). During Part B (MAD), a 1-hour (± 15 minutes) EEG will be collected at screening under sleep deprived conditions (after only 4 hours of sleep) and a 24-hour ambulatory EEG will be collected from at least 30 minutes (± 10 minutes) predose (Day 1) until at least 2 hours post morning dose (Day 2). This will incorporate both pre- and post-Day 2 dosing. On Days 3, 4, 5, and 6, a 2-hour (± 10 minutes) postdose EEG will be collected commencing at least 30 minutes predose until at least 120 minutes post morning dose. On Day 7, a 24-hour ambulatory EEG will be collected from at least 30 minutes (± 10 minutes) predose until 24 hours (± 1 hour) post morning dose (Day 8). Additional EEGs may be performed as deemed necessary and as data emerges from study cohorts.

⁵ During Part B (MAD Cohort3), PK samples will be taken at predose and 30 minutes (± 2 minutes), 1-hour (± 5 minutes), 2-, 4-, 8- (predose for 2nd dose), 8.5-, 9-, 10-, 12- and 16- hours (± 15 minutes) postdose (Days 1 and 7 only). Note that the 8.5-, 9-, 10-, 12 and 16-hour timepoints represent 0.5-, 1-, 2-, 4-, and 8 hours *after* the 2nd dose).

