Subjects will be housed in the clinic from Day -3 prior to study drug administration and will remain in-house for 30 hours postdose (Day 2) for PK and safety assessments.

[figure not shown]
Part B (MAD) will evaluate up to 3 doses based on doses established during Part A (SAD). Each subject will receive 7 doses of study drug, administered either once (Cohorts 1 and 2) or twice daily (Cohort 3). All subjects in each MAD cohort will have their AE, PK, and electroencephalography (EEG) data, acquired up to and including Day 8, evaluated for safety and tolerability by the CRC before opening the next higher dose cohort. Subjects will be housed in the clinic from Day -3 prior to study drug administration and will remain in-house for 24 hours post morning dose (Day 8) for PK and safety assessments.

The study will be comprised of 3 periods: Screening (up to 28 days); Treatment (1 day for the SAD subjects and 7 days for MAD subjects) and Follow-up. Subjects will have a follow-up visit 7 days after the last dose. As SAD dosing is a single dose on Day 1, follow-up will occur

on Day 7. MAD dosing involves either single daily dosing (Cohorts 1 and 2) or twice daily dosing (Cohort 3) on Days 1 to 7, with a follow-up visit occurring on Day 14.

The overall study design is summarized in Figure 1. Refer to Appendix 1 and Appendix 2 for a detailed schedule of assessments.

Figure 1 Study Phases and Activities

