5.3.4. Dose Escalation

An evaluable subject is one that has been dosed, completed all assessments, and had their data reviewed by the CRC.

Blinded data to be reviewed by the CRC for each subject will include (as a minimum): PK (up to 30 hours postdose for Part A and 24 hours postdose for Part B), EEG, ECG, vital signs, pulse oximetry, neurological examination, and any adverse events.

The CRC may approve dose escalation following review of cohort data if:

- No drug related SAE's occurring within 48 hours of administration of KNX100 or placebo is observed in any subject in the dose group under evaluation.
- No drug related AE's of Grade 3 or greater are observed in 2 or more subjects within a dose group.
- The mean KNX100 C_{max} **OR** AUC does not exceed 84.9 ng/mL or 82.7 ng×h/mL respectively **and** the mean KNX100A C_{max} **OR** AUC does not exceed 26.5 ng/mL and 45.7 hr × ng/mL, respectively, the exposure associated with 1/10th of the NOEL of 2.75 mg/kg observed in the 14-day dog EEG study.
- No emergence or evidence of other PI-deemed and or medical monitor-deemed clinically significant abnormal vital signs, neurological and physical examination, or safety parameters postdose have been observed.

Dose increases will be permitted once review of data from all evaluable subjects has been performed.

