8.5.2. Secondary Pharmacokinetic Endpoints

The secondary PK endpoints include:

- Maximum observed concentrations (C_{max}) following dose administration.
- Time of C_{max} (T_{max}) following dose administration.
- Area under the concentration-time curve (AUC) from time zero to last quantifiable concentration (AUC_{0-last}), from time zero to 24 hours postdose administration (AUC_{0-24}), and, as data permit, from time zero to extrapolated to infinity ($AUC_{0-\infty}$).
- As data permit, additional disposition parameters including terminal half-life ($t_{1/2}$), volume of distribution (V_z/F), and oral clearance (CL/F) may be calculated.
- Accumulation ratio (RAC) for C_{max} and AUC_{0-24} ; Day 7 vs Day 1 (MAD phase only).
- Other PK parameters will be calculated as deemed appropriate and as referred to in [Section 8.7](#).

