8.7. Statistical Analysis of Pharmacokinetic Variables

PK endpoints for this study are provided in [Section 8.5.2](#). PK concentrations and parameters will be listed and summarized by dose, treatment group, and measurement time using appropriate descriptive statistics. The actual sampling times will be used in the parameter calculations, and PK parameters will be derived using standard non-compartmental methods. Where possible, the following PK parameters of KNX100 and any measurable metabolites will be determined:

- Following the single-dose part of the study:
 - Maximum plasma concentration (C_{max}), time to C_{max} (T_{max}), terminal rate constant (λ_z), terminal half-life ($t_{1/2}$), area under the plasma concentration-time curve from zero to 24 hours (AUC_{0-24}), from zero to the time of the last measurable concentration (AUC_{0-t}) and from zero to infinity ($AUC_{0-\infty}$), apparent plasma clearance (CL/F), apparent volume of distribution (V_z/F), mean residence time (MRT).
- Following the multiple-dose part of the study:

- Maximum plasma concentration (C_{\max}), time to maximum C_{\max} (T_{\max}), minimum plasma concentration (C_{\min}), area under the plasma concentration-time curve from zero to the end of the dosing interval (AUC_{0-24}) will be assessed on both Day 1 and Day 7. The apparent oral plasma clearance (CL/F), the apparent volume of distribution (Vz/F), the terminal $t_{1/2}$, and the AUC extrapolated to infinity will be calculated on Day 7 (and Day 1 if data permit). The extent of accumulation following multiple dosing (accumulation ratio [RAC]) will be evaluated for C_{\max} and AUC_{0-24} .

The C_{\max} and T_{\max} parameters will be determined through the concentration-time profiles. Where possible, the λ_z will be calculated by log-linear regression of the terminal portion of the concentration-time profiles where there are sufficient data and the $t_{1/2}$ will be calculated as $\ln 2/\lambda_z$. The AUC_{0-t} and the AUC_{0-24} will be calculated using the linear trapezoidal rule. Where appropriate, the AUC_{0-t} will be extrapolated to infinity using λ_z to obtain AUC_{INF} . The AUC will be calculated using the linear trapezoidal rule. CL/F will be determined as $\text{dose}/AUC_{\text{INF}}$. Vz/F will be determined as $\text{Dose} / (AUC_{\text{INF}} * \lambda_z)$.

Where possible, the appropriate PK parameters will also be determined for the metabolite (s) of KNX100.

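### Part B names AUC0-24 and its Day 7/Day 1 accumulation ratio as endpoints, but no 24 h PK sample is listed for Day 1, and the documents contradict each other on the Day 8 sample

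*Protocol*

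**What the plan says.** **What is required at 24 h.** Protocol 8.5.2 lists as a secondary endpoint "Accumulation ratio (RAC) for C_{max} and AUC_{0-24} ; Day 7 vs Day 1 (MAD phase only"; SAP section 2 repeats it. Protocol 8.7 says the Part B area "from zero to the end of the dosing interval (AUC_{0-24}) will be assessed on both Day 1 and Day 7", and that AUC0-24 "will be calculated using the linear trapezoidal rule". Protocol 5.3.4 gives the committee's minimum data as "PK (up to 30 hours postdose for Part A and 24 hours postdose for Part B", and 9.8.1 runs the Part B review to the 24-hour point on Day 8. SAP 4.3 also uses AUC0-24 in defining the PK Set.

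**What is listed.** Appendix 3 footnote 2 ("During Part B (MAD Cohorts 1 and 2), PK samples will be taken at predose and 15 minutes") runs to 12 h on Days 1, 4 and 7 for Cohorts 1 and 2. Footnote 5 ("During Part B (MAD Cohort3), PK samples will be taken at predose and 30 minutes") runs to 16 h after the morning dose, which is 8 h after the second dose, on Days 1 and 7 for Cohort 3. The PK row of Appendix 2 marks Days 1, 4 and 7 only. For Part A, footnote 2 does list 24 h and 30 h.

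**What points the other way.** Appendix 3 footnote 1 makes Day 8 the Part B 24-hour timepoint and says "This visit will be used to collect only the" 24-hour samples. Section 3.1 says subjects "will remain in-house for 24 hours post morning dose (Day 8) for PK and safety assessments", and the synopsis also places PK before the Day 8 discharge.

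**What the SAP derives.** The Part B table in SAP 6.3.1 has AUC0-8, AUC8-16 (Cohort 3) and AUC0-last. It leaves the interval for the AUC accumulation ratio to the quantifiable data and estimates lambda-z on Day 7 only.

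**The concern.** A trapezoidal AUC over 0-24 h needs an observation at or near 24 h. Without one on Day 1, the denominator of a named accumulation ratio is missing for every Part B subject. On Day 7 the outcome depends on which footnote the site follows: staff working from the time lists would not draw the sample, while staff working from footnote 1 would.

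The two days could then be sampled over different lengths. Because the SAP leaves the ratio's interval open, nothing in the plan rules out comparing a longer Day 7 area with a shorter Day 1 area. The SAP's steady-state clearance is dose divided by AUC over the dosing interval. For once-daily dosing that interval is 24 h, so this parameter too depends on the unresolved Day 8 sample.

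**Working it through.** **1. Requirement against schedule.** Part B plans 3 x 8 = 24 subjects, 3 x 6 = 18 of them on KNX100.

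| Day and cohort | Last listed PK time | Share of the 24 h window | Any text implying a 24 h sample |
|---|---|---|---|
| Day 1, Cohorts 1-2 | 12 h (footnote 2) | 12/24 = 50% | none |
| Day 1, Cohort 3 | 16 h (footnote 5) | 16/24 = 67% | none |
| Day 7, Cohorts 1-2 | 12 h (footnote 2) | 50% | footnote 1, section 3.1, synopsis |
| Day 7, Cohort 3 | 16 h (footnote 5) | 67% | footnote 1, section 3.1, synopsis |

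Day 1 is a gap in the text; Day 7 is a contradiction. The SAP plans no Day 1 lambda-z, so it has no route to extrapolate Day 1 to 24 h.

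**2. The protocol's own PK arithmetic (3.2.1).** Dose = CL/F x AUC = 356,000 mL/h x 23.3 h·ng/mL = 8.29 mg, which reproduces the stated 8.3 mg.

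**3. How fast KNX100 appears to clear.** At 20 mg, which 3.2.1 associates with a Cmax of about 46 ng/mL, AUC = 20,000,000 / 356,000 = 56.2 h·ng/mL. AUC/Cmax = 56.2 / 46 = 1.22 h. If the decline were mono-exponential from time zero, the half-life would be ln 2 x 1.22 = 0.85 h.

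**4. Share of Day 1 AUC0-24 after the last listed sample.** The documents give no human half-life, so it is an assumption here, shown over a range. The model is mono-exponential decline from each dose, with k = ln 2 / half-life.

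- Cohorts 1-2: (e^(-12k) - e^(-24k)) / (1 - e^(-24k)).
- Cohort 3, doses at 0 and 8 h: [A(16,24) + A(8,16)] / [A(0,24) + A(0,16)], where A(a,b) = (e^(-ka) - e^(-kb)) / k.

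| Assumed half-life | Cohorts 1-2, after 12 h | Cohort 3, after 16 h |
|---|---|---|
| 0.85 h | 0.006% | 0.07% |
| 1 h | 0.02% | 0.2% |
| 2 h | 1.5% | 3.1% |
| 4 h | 11% | 12% |
| 8 h | 26% | 23% |
| 12 h | 33% | 28% |

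**5. Why the interval must match on both days.** Take once-daily dosing, an assumed 4 h half-life and steady state by Day 7, and scale areas so that the single-dose AUC to infinity is 1. The Day 7 AUC0-24 is then 1. The Day 1 AUC0-24 is 1 - 2^(-6) = 0.984, giving a ratio of 1.016. The Day 1 AUC0-12 is 1 - 2^(-3) = 0.875. Dividing the Day 7 24 h area by that gives 1 / 0.875 = 1.143, so apparent accumulation of about 14% would come almost entirely from unequal windows. With 0-12 h on both days the ratio returns to 1 / (1 - 2^(-6)) = 1.016.

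**The case against.** The strongest reply is that most of this is already handled. The SAP's Part B table uses areas that lie within the sampled times, and the exposure cap in Protocol 6.20.1 is set on Cmax and AUC0-last. On the protocol's figures almost no KNX100 area lies beyond 12 h. Footnote 1 can be read as supplying the Day 8 draw. The footnotes allow sampling times to change, and Protocol 8.7 allows Day 1 terminal parameters if the data permit.

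Much of that stands. It limits the consequence, but it does not remove the inconsistency. AUC0-24 remains the named endpoint in both documents and remains in the PK Set definition. The SAP does not take up the Day 1 option of Protocol 8.7. Permission to alter sampling in response to emerging data does not schedule a sample that an endpoint already needs.

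The Appendix 3 grid cannot settle the matter from the extracted text. As extracted, the Part B 24 h marks fall under EEG. With the one-column shift that makes the 1 h, 8.5 h and 12 h rows agree with the footnotes, they fall under PK for Cohorts 1-2 and for Cohort 3. If the original grid does carry 24 h PK marks, Day 1 also becomes a contradiction with footnotes 2 and 5 rather than a plain gap.

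Three stronger readings are tempting, and the documents do not support them:

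- *The committee's Part B criteria cannot be met.* The escalation criteria concern adverse events, mean Cmax and AUC against the limits, and clinically significant findings. All can be assessed on the listed samples. The 24 h wording describes the data package.
- *The exposure limit is checked on different windows in Parts A and B.* AUC0-last ends at the last quantifiable concentration, so the windows differ only if drug is still measurable after 12 or 16 h, which the documents do not show. The SAP also derives AUC0-8 in both parts.
- *Day 1 Cmin is lost.* The value before the first dose is zero whatever is sampled later.

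**Conclusion.** The point holds in limited form. From the listed times, Day 1 AUC0-24 and the AUC0-24 accumulation ratio cannot be computed by the stated linear trapezoidal rule for any of the 18 planned active Part B subjects. For Day 7, the documents contradict each other on whether a Day 8 24 h PK sample is drawn. It would be too broad to say that Part B endpoints in general are lost: Cmax, Tmax, AUC0-last, the Cmax accumulation ratio and the exposure cap are unaffected.

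For KNX100 the numerical loss is probably negligible. At the half-life of about 0.85 h implied by the protocol's figures, the uncovered tail is under 0.1%. That figure assumes a single exponential and would understate the tail if there is a slower terminal phase. For KNX100A, which has its own exposure limits, the documents give no half-life, so losses of 11% to 26% (assumed half-lives of 4 to 8 h, Cohorts 1-2) are neither shown nor excluded. The finding rests on the footnote lists and the Appendix 2 PK row; the original grid should be checked before amending.

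**What to change.** Reconcile the Appendix 3 grid, its footnotes 1, 2 and 5, and the Appendix 2 PK row with the endpoints, in one of two ways.

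(a) List a 24 h PK draw for Day 1 (before the Day 2 dose) and for Day 7 (at the existing Day 8 visit) in footnotes 2 and 5 and in the Appendix 2 PK row. Cost: two blood draws per subject, both while the subject is already in-house.

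(b) Restate the Part B AUC and accumulation-ratio endpoint in Protocol 8.5.2 and 8.7 and SAP sections 2 and 4.3 over one fixed, sampled interval that is identical on Day 1 and Day 7. Candidates are the SAP's AUC0-8, or 0-12 h in Cohorts 1-2 and 0-16 h in Cohort 3. Replace the SAP's data-dependent interval for the ratio with that choice, and align the PK horizon in Protocol 5.3.4 and 9.8.1 with it. Cost: wording only. For any cohort already sampled to the shorter times, only (b) is available.

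Neither option changes the escalation criteria or the exposure limits.

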5.3.3. Part B Dosing

In Cohorts 1 and 2, study drug will be administered once daily for 7 days at approximately the same time each day \pm 30 minutes. In Cohort 3, study drug will be administered twice daily, approximately 8 hours (\pm 30 minutes) apart for 7 days. Doses will be administered:

- Morning (e.g., at 11:00 am) at approximately the same time (\pm 30 minutes) each day
- Afternoon/ Evening (e.g., at 7:00 pm) at approximately the same time (\pm 30 minutes) each day

The first dose of study drug will be administered together with a glass of tap water under a fasted state i.e., after an overnight fast of at least 10 hours. For MAD Cohort 3, the second dose of study drug will be administered together with a glass of tap water under a fasted state i.e., after fasting for at least 2 hours prior to dose administration. For all cohorts, no food is allowed for at least 2 hours after drug administration. Please refer to [Section 5.10.3](#) for information related to fluid and food restrictions both pre- and postdose.

[Table 4](#) provides the planned dose-escalation schedule for Part B (MAD). Up to 2 dose strengths ranging from as low as 10 mg and up to the clinical exposure cap will be selected based on the tolerability and pharmacokinetics of the previous dose.

Table 4 Planned Dose-Escalation Schedule (MAD Part B)

Cohort	Oral Daily Dose (mg/day) ¹		Total Number of Capsules/Day (Number - Strength) ¹	
	KNX100	Placebo	KNX100	Placebo ²
1	10 (Low)	0	2 capsules (2 × 5 mg)	2 capsules (2 × 0 mg)
2	30 (High)	0	2 capsules (1 × 5 mg, 1 × 25 mg)	2 capsules (2 × 0 mg)
3	30 (bid) ³	0	2 capsules (1 × 5 mg, 1 × 25 mg) (am) 2 capsules (1 × 5 mg, 1 × 25 mg) (pm)	2 capsules (2 × 0 mg) (am) 2 capsules (2 × 0 mg) (pm)

Abbreviations: am = morning; bid = twice daily; MAD = multiple ascending dose; pm = afternoon/evening

¹ Dose levels will be based on data from Part A and emerging PK data.

² An equivalent number of capsules will be administered to subjects receiving placebo.

³ Dose to be administered twice daily, 8 hours apart (refer also to [Section 5.3.3](#)).

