6.20.1. Maximum Clinical Exposure

Clinical PK will be considered as criteria for escalation of clinical doses. Dosing will not exceed $1/10^{\text{th}}$ of the exposure associated with the NOEL of 2.75 mg/kg observed in the 14-day dog EEG study (KNX100 C_{max} and $AUC_{0-\text{last}}$ of 84.9 ng/mL and 82.7 hr \times ng/mL, respectively and KNX100A C_{max} and $AUC_{0-\text{last}}$ of 26.5 ng/mL and 45.7 hr \times ng/mL, respectively).

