Residual area	Percentage of AUC _{0-∞} due to extrapolation from the time of last non-zero concentration to infinity.
DN AUC	Dose-normalized AUC, calculated as AUC/ Dose where AUC is AUC ₀₋₈ and AUC _{0-last}
DN C _{max}	Dose-normalized C _{max} , calculated as C _{max} / Dose

MAD

Parameter (Unit)	Method
C _{max} (ng/mL)	Maximum plasma concentration obtained directly from the observed concentration versus time data, Day 1 and Day 7
AUC _{0-∞} (h*ng/mL)	Area under the plasma concentration-time curve from time zero (pre-dose) extrapolated to infinity (units) calculated by linear trapezoidal rule and extrapolated to infinity by the addition of the last quantifiable concentration divided by the terminal rate constant: AUC _{0-last} + C _{last} /λ _z . Day 7 only
AUC _{0-last} (h*ng/mL)	Area under the plasma concentration-time curve from time zero to the time of the last quantifiable concentration at time "t" (units), over the whole plasma profile on Days 1 and 7, calculated by linear trapezoidal rule. Cohorts 1, 2 and 3
AUC _{0-8h} (h*ng/mL)	Area under the plasma concentration-time curve from time zero to 8 hours after dosing, calculated by linear trapezoidal rule. Days 1 and 7, Cohorts 1, 2 and 3
AUC _{8-16h} (h*ng/mL)	Area under the plasma concentration-time curve from time 8 hours to 16 h after first dose, calculated by linear trapezoidal rule. Days 1 and 7, Cohort 3
T _{max} (h)	Time to maximum plasma concentration obtained directly from the observed concentration versus time data. Day 1 and Day 7
CL/F _{ss} (L/h)	Plasma clearance estimated as dose divided by AUC _{0-tau} . Day 7 only where data permits
V _z /F (L)	volume of distribution estimated by dividing the apparent clearance by λ _z . Day 7 only
λ _z (h ⁻¹)	Apparent terminal elimination rate constant estimated by log-linear least-squared regression of the terminal part of the concentration-time curve profile. Day 7 only
t _{1/2} (h)	Elimination half-life, calculated as ln(2)/λ _z . Day 7 only
Residual area	Percentage of AUC _{0-∞} due to extrapolation from the time of last non-zero concentration to infinity. Day 7 only
RA AUC	Accumulation Ratio for AUC, calculated as AUC _{Day 7} / AUC _{Day 1} , Cohorts 1, 2 and 3 (note the time interval over which the AUC will be determined will be dependent on the quantifiable data).

Parameter (Unit)	Method
RA Cmax	Accumulation Ratio for Cmax, calculated as Cmax Day 7 / Cmax Day 1

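### In MAD Cohort 3 the early samples after the second dose have much wider windows than those after the first, and the SAP defines Cmax, Tmax and RA Cmax by day although it splits AUC by dose.

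*Protocol*

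**What the plan says.** **Sampling.** Protocol Appendix 3, footnote 5, starts the Cohort 3 series with "predose and 30 minutes (± 2 minutes), 1-hour (± 5 minutes". The rest of the series includes "8- (predose for 2nd dose), 8.5-, 9-, 10-, 12- and 16- hours (± 15 minutes) postdose". The footnote adds that the "8.5-, 9-, 10-, 12 and 16-hour timepoints represent 0.5-, 1-, 2-, 4-, and 8 hours" after the second dose. The samples 0.5 h and 1 h after dose 2 therefore carry ±15 min, where those after dose 1 carry ±2 and ±5 min. Later samples carry ±15 min after both doses.

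Footnote 2 gives Cohorts 1 and 2 "predose and 15 minutes (± 2 minutes), 30 minutes (± 2 minutes), 1-hour (± 5 minutes), 2-, 4-, 8-, and 12- hours". Those cohorts have a 15-minute sample. Cohort 3 has none after either dose.

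**Dosing.** Protocol Section 5.3.3: "In Cohort 3, study drug will be administered twice daily, approximately 8 hours", with a tolerance of ±30 minutes.

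**Analysis.** In SAP Section 6.3.1, Table 4 (MAD), Tmax is "Time to maximum plasma concentration obtained directly from the observed concentration versus time data. Day 1 and Day 7". Cmax is defined the same way, and RA Cmax is the Day 7 value over the Day 1 value. None of the three names a dose. The same table gives Cohort 3 separate AUCs for 0-8 h and 8-16 h. The section uses actual elapsed time since drug administration, but does not say which of the two daily doses starts the clock.

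**Use.** Protocol Section 6.20.1: "Clinical PK will be considered as criteria for escalation of clinical doses". Section 5.3.4 sets the mean KNX100 Cmax limit at 84.9 ng/mL.

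**The concern.** A concentration peak that rises and falls within an hour is caught only if the early samples are close to it. A nominal 30-minute sample with a ±15 min window may be drawn anywhere from 15 to 45 minutes after the dose. The two peaks of one day are then measured with different precision, in the cohort with the highest planned daily dose.

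The two doses also differ in fasting (at least 10 h before the first, at least 2 h before the second; Protocol Section 5.3.3), so their peaks may really differ. Twice-daily PK is a secondary objective in its own right (Protocol Section 2.2). If Cmax and Tmax are taken once from the whole-day profile, the report cannot show such a difference, and the summary Tmax averages over two doses.

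**Working it through.** **Inputs, Protocol Section 3.2.1.** CL/F 356,000 mL/h; target AUC 23.3 h×ng/mL; about 20 mg for a Cmax of 46 ng/mL. Sample times and windows are those of Appendix 3.

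**The plan's own figure.** Dose = CL/F × AUC = 356,000 × 23.3 = 8.29 million ng = 8.29 mg, against the stated 8.3 mg. It reproduces.

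**Calibration (assumption).** AUC at 20 mg = 20,000,000 / 356,000 = 56.2 h×ng/mL, so Cmax/AUC = 46 / 56.2 = 0.819 per h. In a one-compartment oral model:

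- Tmax = ln(ka/ke) / (ka − ke)
- Cmax/AUC = ke × exp(−ke × Tmax)

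With r = ka/ke this gives ke = 0.819 × r^(1/(r−1)). For r = 2, ke = 0.819 × 2 = 1.64 per h and Tmax = ln 2 / 1.64 = 0.42 h. The documents give no absorption rate, so r was varied from 1.05 to 15.

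**Simulation.** 100,000 draws per scenario, sample times uniform within their windows, second-dose samples timed from the second dose, equal true peaks after both doses. Recovery = largest sampled concentration / true peak.

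| ka/ke | Tmax (h) | Cohorts 1-2 | Cohort 3 dose 1 | Cohort 3 dose 2 | SD dose 1 / dose 2 | Cohort 3 daily maximum | Dose 2 larger |
|---|---|---|---|---|---|---|---|
| 1.05 | 0.45 | 0.993 | 0.993 | 0.951 | 0.004 / 0.043 | 0.994 | 20% |
| 2 | 0.42 | 0.985 | 0.985 | 0.946 | 0.007 / 0.049 | 0.988 | 29% |
| 4 | 0.36 | 0.958 | 0.947 | 0.920 | 0.012 / 0.076 | 0.965 | 50% |
| 8 | 0.27 | 0.996 | 0.868 | 0.860 | 0.016 / 0.105 | 0.910 | 50% |
| 15 | 0.19 | 0.982 | 0.791 | 0.795 | 0.015 / 0.109 | 0.840 | 50% |

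**Effect of the window.** Dose 1 and dose 2 in Cohort 3 differ only in the windows. Mean loss is 0.993 − 0.951 = 0.042 at the slow end and 0.791 − 0.795 = −0.004 (none) at the fast end. The clearer effect is on spread, from at most 0.02 to 0.04-0.11. At ka/ke = 8, for example, the concentration is 0.998 of the peak at 15 min, 0.868 at 30 min and 0.671 at 45 min. With between-subject variation in ka added (log-SD 0.4), the SD goes from 0.04-0.07 after dose 1 to 0.08-0.12 after dose 2.

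**Effect of the missing 15-minute sample.** Cohorts 1-2 minus Cohort 3 dose 1: 0, 0, 0.011, 0.128 and 0.191. It matters only when Tmax is about 0.27 h or less.

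**Slower peaks (assumption, Tmax 1-2 h).** All three schedules recover 0.96-1.00 and differ by under 1 point.

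**Tmax.** Carry-over at 8 h is below 0.1% of the peak in the calibrated scenarios. With equal true peaks, which dose supplies the daily maximum is a matter of sampling chance. Counted from the first dose, Tmax would then fall near 0.5 h in some subjects and near 8.5 h in others.

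**The case against.** **Size.** The numbers rest on pairing two figures from Protocol Section 3.2.1 in a one-compartment model. The same section gives another pair, a pre-study prediction of 50 ng/mL and 125 ng×hr/mL. Its ratio of 0.4 per h puts Tmax at 0.40-0.92 h, where the Cohort 3 daily maximum recovers 0.98-1.00. The sponsor already had human data and may have chosen the times accordingly, and the schedule may be altered as data emerge. This stands: the loss in mean peak may be negligible.

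**Consequences.** The study is descriptive, and the same schedule on Days 1 and 7 should largely cancel systematic error in RA Cmax. Scaled linearly to 30 mg per dose, the Section 3.2.1 figures give a Cmax of 46 × 1.5 = 69 ng/mL (limit 84.9) and an AUC of 30,000,000 / 356,000 = 84.3 h×ng/mL (limit 82.7). AUC would reach its limit before Cmax, so a small loss in Cmax is unlikely to decide that check. This also stands.

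**Stronger readings that the documents do not support.**

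- A reader might infer that one Cmax per day understates exposure. It does not do so by itself: it takes the larger of two sampled peaks, so its recovery is above that of either dose in every row of the table.
- A reader might infer, from the ±30 min allowed for the second dose, that the 8.5 h and 9 h samples would be drawn on the first-dose clock and could precede the second dose. Footnote 5 makes the 8 h sample a predose sample and equates the later times with hours after the second dose. The wording could be firmer, but a mistimed draw would be a departure from the plan.
- A reader might call the missing 15-minute sample a clear defect. Its cost ranges from nothing to 19 points with an absorption rate that the documents do not give.

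**What remains.** Actual sampling times correct AUC and Tmax for clock error, but they cannot recover a peak that was not sampled. The SAP's silence on dose interval is also untouched by these arguments.

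**Conclusion.** The point holds in modest form. The window contrast is plain in footnote 5, and nothing in the documents explains it. Its cost is mainly added noise in the second-dose peak, with a mean loss of 0 to about 4 points. These figures assume one-compartment profiles calibrated to Protocol Section 3.2.1, uniform timing within windows and equal true peaks. With a peak at 1-2 h the effect is small.

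The Tmax problem depends less on the model. Wherever each dose supplies the larger sample in a fair share of subjects (20-50% of draws here), a whole-day Tmax describes neither dose. That one value per day is intended is the natural reading of Table 4, not a stated rule, so at the least the SAP is unclear.

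**What to change.** 1. **Protocol Appendix 3, footnote 5.** State that samples after the second dose are timed from the actual second-dose time, with ±2 min at 0.5 h and ±5 min at 1 h.
2. **SAP Table 4 (MAD).** For Cohort 3, derive Cmax and Tmax separately for 0-8 h and 8-16 h, with Tmax counted from the dose that starts the interval. Compute RA Cmax for the same interval on Days 7 and 1. Keep the daily maximum as well, for the exposure-limit check.
3. **Optional.** If the human data already in hand show an early peak (about 0.3 h or less), restore the 15-minute sample used in Cohorts 1-2 after each dose.

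Items 1 and 2 change wording only and add no samples. In the calibrated model, item 1 brings the dose-2 SD down to the dose-1 level (at most 0.02), while mean recovery stays at 0.79-0.99. Item 3 adds up to 4 draws per subject (2 doses × 2 days) and would bring mean recovery per dose to 0.96-1.00.
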